APPENDIX 6. PART C PHARMACOKINETIC SAMPLING SCHEDULE

Procedure	Day 1	Week 4	Week 8	Week 12	Week 16	Week 20	Week 24	Week 36	Week 48	Early Termination/ Withdrawal
		Day 28 ± 3 days	Day 56 ± 3 days	Day 84 ± 3 days	Day 112 ± 5 days	Day 140 ± 5 days	Day 168 ± 5 days	Day 252 ± 5 days	Day 336 ± 5 days	
PK Sampling (Plasma and Whole Blood)	15 min to 2 h postdose	Predose ^a	X							
	X	X	X	X	X	X	X	X	X	

^a Can be collected up to an hour prior to dosing.

APPENDIX 8. PART D PHARMACOKINETIC SAMPLING SCHEDULE

Procedure	Day 1	Week 2	Week 8	Week 12	Week 16	Week 24	Week 36	Week 48	Early Termination/ Withdrawal
		Day 14 ± 3 days	Day 56 ± 3 days	Day 84 ± 5 days	Day 112 ± 5 days	Day 168 ± 5 days	Day 252 ± 5 days	Day 336 ± 5 days	
	Sample 1								
PK Sample (Plasma & Whole Blood)	15 min to 2 h postdose	Predose ^a	X						
	X	X	X	X	X	X	X	X	

Abbreviation: PK, pharmacokinetic.

^a Can be collected up to an hour prior to dosing.

## 1. GLOSSARY OF ABBREVIATIONS

AE	Adverse Event
ATC	Anatomical Therapeutic Chemical
BMI	Body Mass Index
CRF	Case Report Form
Cmax	Maximum Blood Concentration
CTCAE	Common Terminology Criteria for Adverse Events
DSMB	Data and Safety Monitoring Board
HU	Hydroxyurea
ICH	International Conference on Harmonisation
MedDRA	Medical Dictionary for Regulatory Activities
NCI	National Cancer Institute
PT	Preferred Term
RBC	Red Blood Cells
SAE	Serious Adverse Event
SAP	Statistical Analysis Plan
SCD	Sickle Cell Disease
SCDSM	Sickle Cell Disease Severity Measure
SD	Standard Deviation
SOC	System Organ Class
TAMM	Time-Averaged Mean of the Maximum
TCD	Transcranial Doppler
TEAE	Treatment-Emergent Adverse Event
TSS	Total Symptom Score
WHO	World Health Organization

## 2. INTRODUCTION AND STUDY OVERVIEW

The purpose of this statistical analysis plan (SAP) is to describe the planned analyses and data displays to be included in the interim Clinical Study Report (CSR) for Protocol GBT440-007. The SAP will describe the analyses for Part A and Part B of the study only.

This SAP was developed in accordance with the ICH E9 guideline. All decisions regarding final interim analysis, as defined in this SAP, will be made prior to database snapshot. Further information can be found in the protocol.

The statistical analysis methods presented in this document will supersede the statistical analysis methods described in the clinical protocol. If additional analyses are required to supplement the planned analyses described in this SAP, they may be completed and will be identified in the CSR.

Planned pharmacokinetic (PK) analyses will be described in a separate analysis plan.

### Study Overview:

This study is a multicenter, open-label study to evaluate the safety, PK and efficacy of GBT440 in pediatric participants with SCD.

This study consists of three parts, Part A, Part B and Part C:

**Part A** is a single dose PK study of GBT440 in pediatric participants with SCD aged 6 to 17 years. This study will involve 2 cohorts in this age range, Cohort 1 (12 to 17 years) and Cohort 2 (6 to 11 years)

**Part B** is a multiple dose, safety, PK and efficacy study of GBT440 in pediatric participants with SCD aged 12 to 17 years, inclusive.

Prior to proceeding from the 900 mg dose to the 1500 mg dose in Part B, the following data reviews will be conducted:

A review of the PK data from at least 8 pediatric participants enrolled in Part B of Study GBT440-007, following at least 15 days of dosing with GBT440 900 mg.

DSMB review of safety data from at least 8 pediatric participants enrolled in Part B of Study GBT440-007, following the completion of 28 days of dosing with GBT440 900 mg to confirm acceptable safety and tolerability.

DSMB review safety data from the first 6 adult participants 1500 mg dose level from Group 1 of Study GBT440-031 (HOPE study), following at least 28 days of dosing with study drug to confirm acceptable safety and tolerability.

**Part C** will assess the safety, tolerability and PK, as well as the hematological effects and the effect on TCD flow velocity of GBT440 in pediatric participants with SCD who are 4 to 17 years of age.

Up to 50 pediatric participants will be enrolled.

- At least 30 participants must have a TCD velocity  $\geq 140$  cm/sec and  $< 200$  cm/sec upon Screening AND
- At least 20 participants must be between 4 to 11 years of age

To further characterize a potential effect on TCD data for those participants who have a TCD velocity  $\geq 140$  cm/sec and  $< 200$  cm/sec upon screening, approximately 20 participants may be added with a TCD velocity of  $\geq 140$  cm/sec and  $< 200$  cm/sec, depending on the emerging data. In this event, Part C will contain up to 70 pediatric participants.

### **3. OBJECTIVES**

#### **3.1. Part A Objectives**

##### **Primary Objective:**

To characterize the PK of GBT440 in plasma and whole blood following a single dose in pediatric participants with SCD

##### **Secondary Objective:**

To evaluate the safety and tolerability of GBT440 following a single dose in pediatric participants with SCD

#### **3.2. Part B Objectives**

##### **Primary Objective:**

The primary objective is to assess the efficacy of GBT440 in pediatric participants with SCD as measured by improvement in anemia

##### **Secondary Objectives:**

- To provide data on the ePRO measurement in establishing the longitudinal measurement properties of the PRO
- To evaluate the effect of GBT440 on clinical measures of hemolysis
- To characterize the PK of GBT440 in plasma, whole blood and red blood cells (RBCs) following multiple doses in pediatric participants with SCD
- To evaluate the safety and tolerability of GBT440 following multiple doses in pediatric participants with SCD
- To evaluate the effect of GBT440 on cerebral hemodynamics as assessed by transcranial Doppler (TCD) ultrasonography
- To evaluate the effects of GBT440 on SCD symptom exacerbation and total symptom score (TSS) from PRO measurement

### 3.3. Part C Objectives

#### Primary Objective:

To evaluate the effect of GBT440 on cerebral hemodynamics in pediatric participants with SCD with elevated or conditional TCD low velocity as assessed by transcranial Doppler (TCD) ultrasonography

#### Secondary Objectives:

- To evaluate the effect of GBT440 on clinical measures of anemia and hemolysis
- To characterize the PK of GBT440 in plasma, whole blood and red blood cells (RBCs) following multiple doses in pediatric participants with SCD
- To evaluate the safety and tolerability of GBT440 following multiple doses in pediatric participants with SCD

## 4. DEFINITIONS AND TERMINOLOGY

#### Study Day

Study Day is defined relative to initiation of treatment, i.e., Day 1. Thus, the study day of an event is calculated as:

$$\text{Study Day} = \text{event date} - \text{Day 1 date} + 1.$$

Day 1 is the date that study drug is first initiated.

#### Study Visit

Study Visit is the nominal visit as recorded on the CRF.

#### Baseline

For all endpoints where both Screening and Day 1 pre-dose assessments are collected, baseline is defined as average of all assessments prior to the first dose. If there is an unscheduled visit prior to first dose, this unscheduled assessment will also be included in the baseline calculation. For PRO endpoints specific to SCD, e.g. TSS, the Baseline value is the average of the non-missing scores during the 28 to 35-day Screening period (Part B).

#### Change from Baseline

Change from baseline to follow-up visit will be calculated as the baseline measurement subtracted from the follow-up measurement for all assessments. Percent change from baseline values to post-baseline values will be calculated using the following formula where applicable:

$$([post-baseline value - baseline value] / baseline value) \times 100\%$$

## Duration of Exposure to Study Drug

Duration of exposure to study drug is defined as the number of weeks from Day 1 to the last date of dosing of Study drug which excludes days where treatment was entirely missed or intermittently stopped as recorded in the CRF. Duration of study drug exposure is calculated as follows:

$$\frac{\sum_{i=1}^n [\text{End Date of Dose}_i - \text{Start Date of Dose}_{i+1}] \times I_{Dose_i}}{7},$$

where  $n$  is the number of dose modifications during the study and

$$I_{Dose_i} = \begin{cases} 0, & \text{if treatment dose } i = 0 \text{ mg} \\ 1, & \text{if treatment dose } i \neq 0 \text{ mg} \end{cases}.$$

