8. DOSAGE AND TREATMENT ADMINISTRATION

8.1. Treatment Regimen

In Part A, participants will receive a single oral dose of voxelotor 600 mg (two 300 mg capsules or tablets).

In Part B, participants will receive voxelotor administered each day for 24 weeks (168 days). Voxelotor will be administered as 300 mg capsules or tablets.

In Part C, participants will receive voxelotor administered each day for 48 weeks (336 days). Participants who are between 12 to 17 years of age will receive voxelotor, 1500 mg/day as dispersible tablets or powder for oral suspension. Participants who are between 4 to 11 years of age will receive voxelotor 1500 mg/day EQUIVALENT as dispersible tablets or powder for oral suspension based on body weight. Either dispersible tablets (100 or 300 mg) or powder for oral suspension (300, 400, 600, or 900 mg) will be used based on [Table 3](#).

In Part D, participants will receive voxelotor administered each day for 48 weeks (336 days). Participants will receive voxelotor 1500 mg/day EQUIVALENT as powder for oral suspension based on body weight. Voxelotor powder for oral suspension (300, 400, 600, or 900 mg) will be used based on [Table 3](#). If powder for oral suspension is not available, dispersible tablets will be used and will be supplied as 100 or 300 mg tablets.

Instructions for administration of study drug for capsules (Part B):

- Voxelotor will be self-administered by the participant in the morning. When necessary, a parent or guardian may be present to assist with this process.
 - except on study visit days when the participant must not take study drug at home. It will be administered at the site after completion of appropriate assessments.
- Participants should take voxelotor with water or other non-alcoholic beverage.

Instructions for administration of study drug as dispersible tablets or powder for oral suspension (Parts C and D):

- Details regarding the dosing preparation and oral administration of the dispersible tablets or powder for oral suspension are provided in the Pharmacy Manual (provided separately).
- For younger participants, voxelotor administration should be supervised by a parent or guardian. Detailed instructions will be provided to participants and their caregivers/legal guardians prior to the first dose of study drug.

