8.2. Dose Modification for Parts B, C, and D

Participants should adhere to their assigned dose level. However, dose modification may be considered if warranted and as outlined below in Section 8.2.1, Section 8.2.2, and Section 8.2.3.

All instances of study drug modification (dose reduction, interruption, increase, or discontinuation) are to be captured in the participant research record and on the CRF, and the Medical Monitor should be notified within 72 hours. If the conditions/event leading to a dose modification have resolved, the original dose level should be resumed, unless in the judgment of the Investigator, this cannot be done safely.

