### **8.3.1. Summary of Exposure**

Study drug administration in Part B will be summarized with number and percentage of participants receiving from 1 to the maximum number of doses by treatment group. Similarly, the duration of study drug exposure will be summarized with descriptive statistics.

The number and percentage of subjects who permanently discontinued study drug, and the reason for discontinuation (adverse event (AE) or other) will be summarized. The number and percentage of subjects who missed at least 1 dose of study drug or had at least 1 dose reduction will be summarized. The summary will include the number and percentage of subjects who had a dose reduction or dose interrupted due to an adverse event or other. Additionally, the number and percentage of subjects will be summarized in categories of number of interrupted doses and number of dose reductions.

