## Exposure to Study Drug

Duration of exposure to study drug is defined as the number of weeks from Day 1 to the last date of dosing of Study drug. The derivation is as follows:

$$(\text{Last dose date} - \text{First dose date} + 1)/7$$

Actual exposure to study drug is defined as the number of weeks from Day 1 to the last date of dosing of Study drug which excludes days where treatment was entirely missed or intermittently stopped as recorded in the CRF. The derivation is as follows:

$$(\text{Last dose date} - \text{First dose date} - \text{Number of days study drug was not taken} + 1)/7$$

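### The Part A/B SAP exposure formula omits the last dosing interval, so a Part B participant with no dose modification gets 0 weeks of exposure

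*SAP*

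**What the plan says.** The Part A/B SAP, section 4 (Duration of Exposure to Study Drug), opens with a verbal definition: exposure is "the number of weeks from Day 1 to the last date of dosing of Study drug", and it "excludes days where treatment was entirely missed or intermittently stopped as recorded in the CRF". A formula follows. It sums a difference of dates over i = 1 to n, multiplies each term by an indicator that is 0 for a 0 mg dose and 1 otherwise, and divides by 7. The text below the formula says that n "is the number of dose modifications during the study".

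The SAP does not say that the starting dose counts as a modification. Protocol section 8.2 describes what is recorded as one: "All instances of study drug modification (dose reduction, interruption, increase, or discontinuation". The starting dose is not on that list.

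The variable is used in section 8.3.1 of the same SAP, which for Part B says that "the duration of study drug exposure will be summarized with descriptive statistics". The matching output is Table 14.1.7.b in section 11.3. Section 2 of this SAP gives its methods precedence over those in the protocol.

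The Part C SAP (section 4, Exposure to Study Drug) reaches the same quantity by another route: "Actual exposure to study drug is defined as the number of weeks from Day 1 to the last date of dosing", again without the days off drug. Its derivation is (last dose date − first dose date − days not taken + 1)/7. The Part D SAP (section 5) uses the same derivation. Neither refers to a count of modifications.

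**The concern.** Each dose modification ends one dosing interval and starts another, so k modifications divide the treatment period into k + 1 intervals. A sum that stops at n = k leaves out the last. With no modification the sum has no terms and equals zero. The formula therefore fails first in the simplest case: a participant who took the assigned dose throughout.

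At stake is the Part B table of exposure duration. If it were programmed literally, unmodified participants would appear as having no exposure, and most modified participants would lose the time after their last change. The SAP would also contradict itself within one definition, leaving the programmer to choose between the words and the formula.

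**Working it through.** The plan states no exposure figure, so there is nothing to reproduce first. The check applies the formula to hypothetical Part B dosing records and compares the result with the verbal definition beside it.

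**Inputs**
- Dosing period: "In Part B, participants will receive voxelotor administered each day for 24 weeks (168 days" (protocol section 8.1), so Days 1 to 168.
- n: the number of changes after the starting dose (Part A/B SAP section 4, with protocol section 8.2). The number of dosing records is n + 1. A hold and its resumption are counted as two changes.
- Day 85, Day 29, Day 57 and the 5-day hold are illustrative choices.

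**Formulas**
- Verbal definition: the sum of (End − Start + 1) over all records with a non-zero dose, divided by 7.
- SAP formula, charitable reading: the sum over i = 1 to n of (End_i − Start_i + 1) × I_i, divided by 7. This assumes that the printed i+1 is a displaced "+1" day.

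**Calculation**
1. No modification, n = 0. Verbal: (168 − 1 + 1)/7 = 24.0. Formula: empty sum = 0.
2. One reduction at Day 85, n = 1. Verbal: (84 + 84)/7 = 24.0. Formula: 84/7 = 12.0.
3. Hold on Days 85 to 89, then resumed, n = 2. Verbal: (84 + 79)/7 = 163/7 = 23.29. Formula: (84 + 0)/7 = 12.0.
4. Reduced at Day 29, original dose resumed at Day 57, n = 2. Verbal: (28 + 28 + 112)/7 = 24.0. Formula: (28 + 28)/7 = 8.0.
5. Permanent stop at Day 85, counted as a modification and followed by a 0 mg record, n = 1. Verbal: 84/7 = 12.0. Formula: 84/7 = 12.0.

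| Case | n | Verbal definition (weeks) | Formula (weeks) |
|---|---|---|---|
| No modification | 0 | 24.0 | 0 |
| One reduction, Day 85 | 1 | 24.0 | 12.0 |
| 5-day hold, resumed | 2 | 23.29 | 12.0 |
| Reduced Day 29, resumed Day 57 | 2 | 24.0 | 8.0 |
| Permanent stop, Day 85 | 1 | 12.0 | 12.0 |

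In case 5 the omitted record is 0 mg and the indicator would remove it anyway, so nothing is lost.

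**Check of the correction.** With n set to the number of records and the term End_i − Start_i + 1, the five results are 24.0, 24.0, 23.29, 24.0 and 12.0, which match the verbal definition in every case. The Part C/D derivation agrees: for case 1, (168 − 1 − 0 + 1)/7 = 24.0; for case 3, (168 − 1 − 5 + 1)/7 = 23.29.

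**The case against.** The strongest defence is that the intent is clear. The correct definition stands directly above the formula, a result of 0 weeks for a compliant participant would be noticed at once, and a competent programmer would probably take n as the number of dosing records. That stands as a reason to rate the point as small. It does not make the formula right, because a specification should not rely on being overridden.

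A second defence is that n is wrong only together with the lower limit of 1; a sum from i = 0 would have n + 1 terms. That is true, and the equation was read by a program. But the lower limit shown is 1, and nothing in the documents supports 0.

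A third is that the end of treatment might itself count as a modification, which would restore the missing interval. Protocol section 8.2 lists discontinuation, but section 8.1.1 of the Part A/B SAP separates participants who completed treatment from those who discontinued it, so a completer has no such event.

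A reader might also infer more than the documents support:
- *That durations come out negative.* Taken literally, the printed subscript subtracts the start of the next interval from the end of the current one. That gives −1 day (−0.14 weeks) in case 2. The subscript may be an extraction artefact, and the point does not depend on it.
- *That every participant is wrong.* Case 5 shows otherwise on the charitable reading.
- *That adverse event rates are distorted.* Section 8.3.2 of the Part A/B SAP plans event counts and participant percentages, with no exposure-adjusted rate. The person-year denominators in the Part C and Part D SAPs run from first to last dose and do not use this formula.
- *That other parts share the error.* Part A is a single dose with no exposure table listed. The Part C and Part D SAPs have the correct derivation.

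**Conclusion.** The point holds as a specification error of limited reach. As written, the Part A/B formula leaves out the last dosing interval and contradicts the definition it is meant to implement. A Part B participant with no modification gets 0 instead of 24 weeks, whichever way the subscript is read. One reduction at Day 85 gives 12 instead of 24 weeks on the charitable reading. A participant whose final record is 0 mg is unaffected on that reading.

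The consequence is confined to the descriptive duration statistics in Table 14.1.7.b. Section 8.3.1 also summarises doses received, missed doses, reductions and interruptions, so duration is not the only exposure information.

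The conclusion assumes that the sum starts at i = 1, as shown, and that the starting dose is not a modification, as protocol section 8.2 implies. The documents do not show which rule the table program used.

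**What to change.** Change one definition in section 4 of the Part A/B SAP, in either of two ways:

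1. Define n as the number of dosing records, including 0 mg records (modifications + 1), with the term End_i − Start_i + 1.
2. Use the Part C/D actual-exposure derivation, (last dose date − first dose date − days not taken + 1)/7. This also aligns the terms: the Part C and Part D SAPs use duration of exposure for the figure that includes gaps, while the Part A/B SAP gives that name to the figure that excludes them.

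Check the i+1 subscript and the lower limit of the sum against the source file at the same time. If Table 14.1.7.b is already programmed, confirm that its code follows the verbal definition. The cost is one line of text and a short program check; no data collection or other analysis changes.

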## Total Symptom Score (TSS)

For each participant, the TSS will be computed as follows: The Baseline TSS is the average of the scores during the 35 Screening period, i.e. the sum of non-missing TSS scores divided by the number of non-missing diary entries. Participants in Part B must complete a minimum of 14 days during Screening with ePRO to be enrolled in the study. During the treatment period when there is at least or 75% compliance during a 4-week period, the TSS is the average score for each 4-week period on treatment. The 4-week periods are Weeks 1-4 (Study Day 1-28), Weeks 5-8 (Study Day 29-56), Weeks 9-12 (Study Day 57-84), Weeks 13-16 (Study Day 85-112), Weeks 17-20 (Study Day 113-140), Weeks 21-24 (Study Day 141-168), and Weeks 25-28 (Study Days 169-196). If lack of compliance is due to missed diary entries or participant dropout, the TSS will be set to missing for that 4-week period or that 4-week period and beyond, respectively.

## Concomitant Medications

Concomitant medications are those medications taken on or after the initiation of study drug. This definition includes medications started prior to the initiation of study drug, but continuing concurrently with study drug.

## Prior Medications

Prior medications are those medications taken prior to the initiation of study drug.

## Treatment-emergent Adverse Event

A treatment-emergent adverse event (TEAE) is defined as an AE that emerges on or after initiation of study drug (having been absent pre-treatment), or an AE that existed pre-treatment and worsened on treatment (relative to the pre-treatment state) through 28 days after study drug discontinuation. AEs occurring on Day 1 are assumed to be treatment-emergent.

## 5. STUDY ENDPOINTS

### 5.1. Part A Endpoints

#### Primary Endpoint:

- $C_{max}$ , area AUC from time 0 to the time of the last quantifiable concentration (AUC0-last) and AUC0-inf of GBT440 in whole blood

#### Secondary Endpoints:

- $C_{max}$ , AUC0-last and AUC0-inf of GBT440 in plasma and RBC
- The time that  $C_{max}$  was observed ( $t_{max}$ ), terminal elimination half-life ( $T_{1/2}$ ) in RBC, whole blood and plasma, and percent Hb occupancy

#### Safety Endpoints:

- Treatment-emergent adverse events (TEAEs) and serious adverse events (SAEs)
- Clinical laboratory tests, physical examination findings, vital signs and ECGs

### 5.2. Part B Endpoints

#### Primary Endpoint:

- Change from baseline to Week 24 in Hb

#### Secondary Endpoint:

- Proportion of days with SCD symptom exacerbation during the first 24 weeks of treatment.
- Change from Baseline to Weeks 21–24 in the (SCDSM) TSS
- Change from baseline to 12 and 24 weeks in LDH, indirect bilirubin and reticulocyte count
- GBT440 PK ( $C_{max}$ , AUC0-last, AUC0-inf, AUC0-24,  $T_{1/2}$ , accumulation ratio, blood/plasma ratio, RBC/plasma ratio, if appropriate) and percent Hb occupancy
- Change from baseline to 12 and 24 weeks in cerebral blood flow as measured by the TAMM TCD velocity

